1. PROTOCOL SUMMARY

1.1 Questions addressed

How many patients might benefit from the XSTAT[®] device, in the civilian setting? How many patients could be enrolled into a trial? What are the baseline estimates of possible future primary and secondary outcomes for a full randomized clinical trial? Is the XSTAT[®] device easy to use, in the prehospital setting? How does the XSTAT impact operative management of penetrating junctional injuries and are the sponges easy to remove? Is the use of the XSTAT[®] device associated with adverse effects?

1.2 Eligible population

Patients aged 15 years and over, or with an estimated body weight of 50kg or more; who have suffered a penetrating junctional injury (femoral or axillary) with visible bleeding; who a suffering from class 3 or 4 hemorrhagic shock; and who will be taken directly to a level I trauma center participating in the PhoXSTAT trial.

1.3 Interventions

Standard prehospital care plus XSTAT[®], compared with standard prehospital care.

1.4 Outcome assessment

We will assess feasibility of a future efficacy/effectiveness trial, and usability and safety of the XSTAT[®] device.

1.5 Coordination

Local: By investigators and research assistants in participating trial sites. Central: By Trial Office at UAB.

3. INTRODUCTION

3.1 Background

3.1.1 Trauma is a major public health issue

Trauma is the leading cause of death for people ≤45 years of age and is the third leading cause of death in the United States (US) overall. Trauma accounts for 41 million Emergency Department (ED) visits and 2 million hospital admissions in the US each year, with an economic burden of more than \$585 billion.(1)

Among the injured, hemorrhagic shock is a leading cause of early death, and is responsible for over 35% of prehospital deaths and 40% of deaths within the first 24 hours after injury.(2) Hemorrhage control is of paramount importance in preventing battlefield mortality and is the top priority of the US military.(3) In a study of injuries from Operation Iraqi Freedom and Operation Enduring Freedom, hemorrhage accounted for 82% of potentially survivable casualties.(4)

3.1.2 Junctional bleeding is particularly challenging, and currently available treatments are unsatisfactory

Junctional bleeding is hemorrhage occurring at the junction of two anatomically distinct regions. The PhoXSTAT trial will specifically investigate injuries to the axillary or femoral regions. These injuries are associated with high mortality. A National Trauma DataBank analysis of 120 isolated femoral arterial injuries revealed a mortality rate of 7.5%. (5)

Bleeding from a junctional injury is difficult to control. Currently available treatments include tourniquets, direct and indirect pressure, and hemostatic dressings. These are unsatisfactory (21 CFR 50.24(a)(1)) because

- a) A tourniquet cannot be applied to these body regions: Junctional injuries are too proximal to permit the application of a tourniquet to temporarily occlude blood flow. It is not possible to occlude the iliac (for femoral arterial injuries) or subclavian (for axillary arterial injuries) arteries with a tourniquet.
- b) Indirect pressure on proximal vessels is ineffective. (6) For the same reasons, it is not possible to provide effective digital compression of the iliac or subclavian arteries.

- c) Direct pressure is ineffective, particularly in deep wounds. (6) Penetrating injuries to the junctional vasculature are difficult to control with direct pressure. Inserting digits into these types of wounds can also exacerbate bleeding, by causing further injury to vascular structures.
- d) Existing hemostatic agents have important practical drawbacks that limit their effectiveness with junctional injuries. For example, junctional injuries often involve deep vascular structures that cannot be easily accessed from the skin surface. Hemostatic bandages inserted through small skin wounds cannot effectively compress deep vascular structures. Similarly, hemostatic powder applied through a small skin wound will not adequately coat deep vascular structures. Hemostatic powders are also difficult to remove during definitive vascular repair.

There are few effective treatment options for junctional injuries other than operative control – which is rarely available in the prehospital setting. Current body armor also does not adequately protect junctional regions. In recent US military efforts, junctional injuries contributed to >70% of potentially survivable casualties.(4)

3.2 XSTAT[®] – A Novel Hemostatic Approach to Junctional Injuries

XSTAT[®] (RevMedx[™], Wilsonville, Oregon) is a novel hemostatic device with features potentially well suited to junctional hemorrhage control.(6)

3.2.1 Mechanism of action

The XSTAT[®] device injects small, rapidly-expanding cellulose sponges into the wound cavity using a syringe-like delivery system. In the wound, XSTAT[®] sponges expand and swell to fill the wound cavity, within 20 seconds of contact with blood, facilitating compression of bleeding structures. XSTAT[®] can be applied through skin wounds. The system can readily access deep vascular structures. While rapidly hemostatic, the hemostatic sponges are also relatively easy to remove. In the setting of junctional bleeding, XSTAT[®] may allow for hemostatic pressure generation from within the wound tract rather than from external compression (as with a tourniquet or manual compression).

3.2.2 Why the XSTAT 12 device may be better than existing available therapies

The XSTAT 12 device may be better than existing available therapies because of its mode of application: The device allows the delivery of the hemostatic component (the sponges) close to the site of bleeding, using the injector. This is particularly helpful for ballistic injuries, where the wound may be relatively small. The device is easily inserted into the wound tract, and directed towards the bleeding femoral or axillary artery – even if the arterial injury is out of reach of tourniquets, direct or indirect pressure, or hemostatic dressings.

3.2.3 Operational philosophy

Hemorrhage should be controlled as early as possible, ideally before reaching a trauma center or medical treatment facility. Given its small size, low weight, and ease of application, the XSTAT[®] device is well-suited for prehospital use, in both the civilian and military setting, and this is probably where the device's applicability lies.

There would appear to be less justification for the use of XSTAT[®] in the setting of a trauma center, where patients can be taken directly to an operating room, or have bleeding controlled by other means.

3.2.4 Current evidence

Although efficacious in animal studies, there have been few studies of the XSTAT device in humans. A recent ten-patient case series, eight of whom had arterial injuries, and two of whom had venous injuries or soft-tissue bleeding, showed that XSTAT appeared to control bleeding well. Overall, half were junctional injuries. XSTAT was able to stop bleeding in nine of ten patients on the first deployment, with the remaining patient requiring one repeat injection. There were no technical device failures or embolic complications.(7)

3.3 Rationale for this trial

3.3.1 The need for further study

XSTAT[®] is approved by the US Federal Drug Administration (FDA) for application in battlefield and civilian trauma patients. However, other than the case series described above,(7) there have been no supporting human evaluations of XSTAT[®]. There is an

urgent need for data to demonstrate the safety and efficacy of the device, prior to recommending its widespread use in the prehospital setting.

3.3.2 The need for a pilot trial

Before a full-scale trial can be conducted, the feasibility of conducting such a study, and the planning assumptions underlying it, will need to be confirmed. The key issues which such a pilot trial needs to address are:

- a) The number of penetrating junctional zone injuries encountered in the prehospital civilian setting.
- b) The feasibility of randomizing patients in the prehospital setting.
- c) Usability.
- d) Safety.
- e) Validation of the proposed primary outcome of an efficacy trial.

4. AIM AND OBJECTIVES

4.1 Aim

The aim of the PhoXSTAT trial is to evaluate the feasibility of conducting a randomized clinical trial of the XSTAT[®] device, in the prehospital setting.

4.2 Objectives and research questions (RQ)

The objectives of the PhoXSTAT trial are:

4.2.1 Trial feasibility

- Objective 1: To evaluate the number of patients with penetrating junctional (femoral and axillary) zone injuries that can be entered into a trial (RQ 1: "How many patients that might benefit from the XSTAT[®] device, in the civilian setting, can be entered into a trial?")
- Objective 2: To evaluate possible future primary and secondary outcomes for a full randomized clinical trial, including admission lactate, admission base deficit, and mortality. (RQ 3: "What are the baseline estimates of possible future primary and secondary outcomes for a full randomized clinical trial?")

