6.3.2 Trial intervention packs

Each EMS vehicle randomly receives a pre-packaged, sealed, numbered trial intervention pack, consisting of a durable plastic case, which either contains either two XSTAT[®] devices, or is empty. The pack remains on the vehicle until used or expired. When a suitable patient meeting the inclusion criteria for the trial is identified by the EMS providers, the pack is opened. If it contains the device, it is used. Once a pack has been used, it is replaced (when the vehicle returns to its base location).

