6.3.3 Tracking labels

The trial intervention packs also contain a tracking label, which must be attached to the patient, to ensure that the trauma center is a) made aware of the patient's enrollment; and b) able to identify which treatment was administered. The tracking label is also used to collect a small amount of prehospital data.

This mechanism avoids having to access a randomization mechanism in real-time and having to carry multiple packs. The disadvantage is that, should a crew encounter more than one suitable patient per shift, some patients may be missed. In addition, in a small study, there is a possibility that, purely by chance, eligible patients may be preferentially encountered by EMS units randomized to either the intervention, or the control treatment. This risk will be reduced with a larger sample size.

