8.3 Patients entered into pilot trial: Prehospital data collection

The PhoXSTAT trial requires the collection of a minimal amount of prehospital data – primarily relating to the usability and safety of the device. Each trial intervention pack contains a tracking label, which must be attached to the patient, using the cable tie supplied. The tracking label contains a mini-questionnaire. If the patient was allocated to treatment with Xstat, the following details must be completed:

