8.4.1 Physiological parameters

The following measurements are collected on admission:

- a) Systolic, diastolic, and mean blood pressure
- b) Heart rate
- c) Shock index
- 8.4.2 Usability

The ease of sponge removal

- a) Unable to remove all sponges
- b) Reasonably easy to remove all sponges
- c) Sponges easily removed

The time required to remove the sponges

- a) 1 hour or longer
- b) Between 5 and 59 minutes
- c) Less than 5 minutes

The use of x-rays/image intensifiers to ensure complete removal of the sponges

- a) Imaging not used due to patient's clinical condition
- b) Imaging not used as not available
- c) Imaging deemed unnecessary
- d) Imaging used

Outcome of imaging:

- a) Additional sponges seen on imaging
- b) No additional sponges seen on imaging

Overall satisfaction with the device

- a) Dissatisfied
- b) Neither satisfied nor dissatisfied
- c) Satisfied

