8.4.3 Blood tests

The following blood tests, which are all measured routinely as part of the clinical assessment of trauma patients, are collected, as soon as possible after admission:

- a) Blood lactate level (from arterial or venous blood gas measurement)
- b) Blood base deficit (from arterial or venous blood gas measurement)
- c) Hemoglobin/hematocrit, platelet count
- d) Prothrombin time (PT)/international normalized ratio (INR), activated partial thromboplastin time (APTT)/ratio
- e) Thromboelastograph (TEG) or thromboelastogram (ROTEM), if available

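### No pre-treatment physiological measure of shock is scheduled in either arm in the legible protocol text, so shock at entry cannot be compared between arms or used to adjust the candidate endpoints

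*Protocol*

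**What the plan says.** Objective 2 (Protocol 4.2.1) is "To evaluate possible future primary and secondary outcomes for a full randomized clinical trial, including admission lactate, admission base deficit, and mortality".

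Protocol 6.2.1 makes class 3 or 4 hemorrhagic shock an entry criterion. EMS crews identify the patient and open the pack, and 6.3.2 then says of the pack: "If it contains the device, it is used". Entry and treatment both precede arrival at hospital.

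Physiology is scheduled later. For blood pressure, heart rate and shock index, 8.4.1 states "The following measurements are collected on admission". The blood tests in 8.4.3, including lactate and base deficit, "are collected, as soon as possible after admission". Table 1 ticks blood pressure, heart rate, lactate and base deficit in the admission column only.

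On the prehospital side, 8.3 says the trial "requires the collection of a minimal amount of prehospital data", "primarily relating to the usability and safety of the device". The label questionnaire is conditional on arm: "If the patient was allocated to treatment with Xstat, the following details must be completed". Table 1 ticks the prehospital column only for safety and usability, and the sample label in Appendix 1 has no vital signs.

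In the codebook (Appendix 2), Form 1, for arrival in the ED, holds one set of first available vital signs and GCS, plus mechanism and demographics. Form 2 lists three inclusion items (fields 47 to 49: age, direct from scene, junctional injury) before the exclusions start at field 50. Form 11 collects the Injury Severity Score. Neither Form 1 nor Form 11 is conditional on arm.

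**The concern.** The variable that defines the population, depth of shock at the scene, has no scheduled value in either arm. A statistical analysis plan can choose covariates, but it cannot adjust for something that was not collected. The admission vital signs cannot stand in for it. XSTAT or control care has already been given by then, so adjusting for them could remove part of any device effect. Nor can the single set on Form 1 serve as both baseline and outcome.

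At stake are how readily the 10.4 comparison can be interpreted at this sample size, and how much the pilot can tell a full trial about lactate and base deficit. Without entry severity, it cannot report what share of endpoint variance entry shock explains, or the residual SD that an adjusted analysis would use.

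**Working it through.** **Scheduled timing of each item**

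| Item | Source | Relative to treatment |
|---|---|---|
| Shock class 3 or 4 | 6.2.1 | Before; not among Form 2 inclusion items |
| Blood pressure, heart rate, shock index | 8.4.1, Table 1 | After |
| GCS | Form 1 | On the arrival form; not marked as prehospital |
| Lactate, base deficit | 8.4.3, Table 1 | After |
| Label questionnaire | 8.3, Appendix 1 | Device items, XSTAT arm only |
| Injury Severity Score | Form 11 | Describes the injury; scored later, anatomical |
| Mechanism, age, sex, weight | Form 1 | Fixed before treatment |

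**Inputs.** The protocol gives no alpha, power, effect size or SD (10.4 says no calculation is required), so there is no plan figure to reproduce. The only figure used from the document is the anticipated maximum of 50 patients (section 9). The equal split of 25 per arm, the case of 12 per arm, and the correlations r between a pre-treatment shock measure and the endpoint are assumptions.

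**Chance imbalance in a baseline measure, in SD units**
- SE = sqrt(2/n per arm) = sqrt(2/25) = 0.283. The 95% range is ±1.96 × 0.283 = ±0.55.
- With 25 per arm, the chance of a difference above 0.25 SD is 38%, and above 0.5 SD it is 8%.
- With 12 per arm, the SE is sqrt(2/12) = 0.408 and the chances are 54% and 22%.

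**What adjustment would gain at N = 50**
- Residual variance factor = 1 − r²
- Adjusted SE = sqrt((2/25) × (1 − r²))
- Equivalent unadjusted sample = 50/(1 − r²)

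| r (assumed) | Variance removed | SE of endpoint difference (SD units) | Equivalent N |
|---|---|---|---|
| none | 0% | 0.283 | 50 |
| 0.3 | 9% | 0.270 | 55 |
| 0.5 | 25% | 0.245 | 67 |
| 0.6 | 36% | 0.226 | 78 |

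One covariate costs one residual degree of freedom (50 − 3 = 47 instead of 50 − 2 = 48).

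**The case against.** Several points on the other side are sound.

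- **Absence is not fully proven.** The codebook text runs from field 52 to field 84. The 31 missing fields, and any Forms 3, 4 and 6, cannot be read, and an EMS form for both arms could be among them. Table 1 is also not exhaustive: GCS, mechanism and Injury Severity Score are on the CRF but not in it. Section 8.3 describes the main purpose of the prehospital data rather than excluding everything else. The point therefore stands only for the legible text.
- **A reader might infer that no severity is collected and no imbalance can be seen.** The forms do not support that. Injury Severity Score, mechanism, age, sex and weight are collected regardless of arm. What cannot be seen is imbalance in physiological shock.
- **A reader might infer bias.** Randomization prevents systematic bias, and an unadjusted confidence interval already allows for chance imbalance. A baseline difference at the 0.55 SD limit with r = 0.5 would shift the endpoint comparison by 0.28 SD, but that variation is already within the 0.283 SE.
- **A reader might take 6.3.3 as an admission of this problem.** Its remark "This risk will be reduced with a larger sample size" concerns which arm's vehicles happen to meet eligible patients. It says nothing about severity and is not relied on here.
- **The trial's goals are modest.** It has no primary outcome and its aim is feasibility. Raw means and SDs answer Objective 2 as written, and an unadjusted SD is a usable, conservative planning input. Restricting entry to class 3 or 4 shock would tend to lower r toward or below the smallest case.
- **Model choice belongs in an analysis plan.** That is so for the covariate and the model. It does not cover values that are never scheduled for collection.

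**Conclusion.** The point holds in a limited form. The legible protocol makes shock at the scene decisive for entry, yet schedules no pre-treatment physiological measure of it in either arm and does not list shock class among the Form 2 inclusion items. Shock at entry therefore cannot be tabulated by arm or used as a covariate in 10.4.

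The loss is in precision, interpretability and planning value, and does not amount to bias or a failure to meet the stated objectives. Its size depends on correlations the document does not give: 9% to 36% of endpoint variance for r from 0.3 to 0.6, or about 5 to 28 patients' worth of information on top of 50. The lower end is quite possible. The conclusion assumes about 25 per arm and that the unreadable codebook fields hold no prehospital vital signs. If they do, what remains is to bring 8.3 and Table 1 into line with the CRF. This is a worthwhile, low-cost improvement and not a fatal flaw.

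**What to change.** - First check codebook fields 53 to 83 for any prehospital vital signs.
- If there are none, add to 8.3, Table 1 and the CRF, for both arms, the first EMS systolic pressure, heart rate, GCS and time. Transcribe them from the EMS record into fields separate from the Form 1 admission values.
- Record shock class at entry on Form 2.
- Report these values by arm. Give the lactate and base deficit comparisons adjusted for pre-treatment shock index beside the unadjusted ones, with raw and residual SDs for planning the full trial. The model details can sit in the analysis plan.
- Keep admission vital signs as outcomes and do not use them as covariates.

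The cost is four transcribed values and one eligibility item for at most 50 patients, plus one covariate. No treatment, consent or randomization step changes. The downside is some missing values where scene contact was short, so the number missing should be reported by arm.

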4.2.2 Device usability

- Objective 3: To evaluate the usability of the XSTAT[®] device, in the prehospital setting, in patients with junctional injuries, in terms of the insertion of the device, and deployment of the sponges. (RQ 4: "Is the XSTAT[®] device easy to use, in the prehospital setting?")
- Objective 4: To evaluate the usability of the XSTAT[®] device, in the operating room setting, in patients with junctional injuries, in terms of the removal of the sponges. (RQ 5: "Are the XSTAT[®] sponges easy to remove, in the operating room?")

4.2.3 Device safety

Objective 5: To evaluate the safety of the XSTAT[®] device, in patients with junctional injuries. (RQ 6: "Is the use of the XSTAT[®] device associated with adverse effects?")

5. DESIGN AND INTERVENTION

5.1 Design

Pragmatic, prehospital, randomized, multi-site, pilot/feasibility trial.

Figure 1. Consort diagram

5.2 Intervention to be evaluated

Patients allocated to the intervention group are treated with standard prehospital care plus XSTAT[®]. The trial will only use the "XSTAT-12" device, which is more suited to the types of injuries seen in civilian practice. XSTAT[®] application will follow the manufacturer's guidance, with injection into bleeding wounds. A sufficient number of sponges are used to fill the injury void. Repeat XSTAT[®] application is performed in the event of persistent bleeding. (The trial packs will contain two devices.)

Figure 2. Xstat device being used to treat right groin wound

XSTAT[®] sponges must be removed surgically. However, all patients with junctional injuries typically undergo operative exploration and repair of vascular injuries. The radiopaque markers embedded in each sponge aid in identification of sponges retained within the body. Each XSTAT[®] device consists of 38 sponges. Because all sponges may not be deployed into the wound or there may be dislodgement from the wound during patient movement, a radiographic survey must be undertaken to identify any retained sponges. The recent cases series by Warriner et al identified retained sponges in two out of ten patients on initial post removal x-rays following wound exploration for definitive hemorrhage control and sponge removal.(7)

It is possible that patients who are initially (in the prehospital setting) thought to have a serious injury, and who are treated with XSTAT, then turn out not to have an injury requiring operative treatment. These patients might have been managed non-operatively, had they not been treated with XSTAT. Determining the number of "forced" or non-therapeutic explorations is a key outcome of this study. However, it is important to recognize that XSTAT is an FDA-approved device, and that this situation can therefore also arise in everyday practice, outwith the context of a trial.

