7.2.2 Operating room (Objective 4)

Use of the XSTAT device commits the patient and medical team to operative exploration of the wound, and retrieval of the sponges. We will evaluate surgeons' views on the device, by collecting data on the following:

- a) The ease of sponge removal
- b) The time required to remove the sponges

- c) The use of x-rays/image intensifiers to ensure complete removal of the sponges
- d) Overall satisfaction with the device

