92	op_venous_repair_1 Show the field ONLY if: [surg_proc_wound(1)] = '1' or ([num_wounds] = '1' and [ope ration_junction_site] = '1')	Patch angioplasty, interposition grafting, or direct repair of venous injury	radio (Matrix) 1 Yes 0 No
93	op_other_details Show the field ONLY if: [surg_proc_wound(1)] = '1' or [[num_wounds] = '1' and [ope ration_junction_site] = '1')	Other operative treatment/additional details:	notes

94	sponges_removed_dt_tm_1 Show the field ONLY If: [randomized_ym] = '1' and [xst _proc_wound(1)] = '1' or ([nu m_wounds] = '1' and [operati on_junction_site] = '1') and [x stat_used_wound_1] = '1'	Section Header: Please describe the experience removing the XSMT sponges from the wound to the (wound, I_side), (wound, I_orientation) (wound, I_olc): What was the date and time at which the sponges were finally removed (or when decision was made that they could not be removed? (M-D-Y H:M)	text (datetime_mdy)	
95	ease_sponge_remove_1 Show the field ONLY If: [randomized_ym] = '1' and [xst a_tatempted] = '1' and [Surg _proc_wound(1)] = '1' or ([nu m_wounds] = '1' and [operati on_junction_site] = '1') and [x stat_used_wound_1] = '1'	Please describe the ease of sponge removal	radio 1 Failed to remove all sponges 2 Reasonably easy to remove all sponges 3 Sponges easily removed	
96	time_sponge_removal_1 Show the field ONLY if: [randomized_ym] = '1' and [xst _tatempted] = '1' and [surg _proc_wound(1)] = '1' or ([nu m_wounds] = '1' and [operati on_junction_site] = '1') and [x stat_used_wound_1] = '1'	Please estimate the time required to remove the sponges	radio 1 31 minutes or longer 2 Between 5 and 30 minutes 3 Less than 5 minutes	
97	Imaging_sponge_removal_1 Show the field ONLY If: [randomized_yn] = '1' and [xst at_attempted] = '1' and [surg _proc_wound(1)] = '1' or ([nu m_wounds] = '1' and [operation on_junction_site] = '1']) and [x stat_used_wound_1] = '1'	Please describe what intraoperative imaging was used to ensure removal of the sponges	radio 1 Imaging not used due to patient's condition 2 Imaging not used, as not available 3 Imaging not used, as deemed unnecessary 4 Imaging used	
98	Imaging_outcome_1 Show the field ONLY if: [randomized_yn] = '1' and [ixagi ng_sponge_removal_1] = '4' and ([surg_proc_wound(1])] = '1' or ([num_wounds] = '1' an d [operation_junction_site] = '1') and [xstat_used_wound_ 1] = '1'	Describe the outcome	radio 1 Additional sponges were seen on imaging 2 No additional sponges were seen on imaging	

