110	sponges_removed_dt_tm_2 Show the field ONLY if: [randomized_yn] = '1' and [xst at_attempted] = '1' and [suta proc_wound(2]] = '1' and [xsta t_used_wound_2] = '1'	Section Header: Please describe the experience removing the XSIAT sponges from the wound to the [wound,2,ide], [wound,2, orientation] [wound,2,loc]: What was the date and time at which the sponges were finally removed (or when decision was made that they could not be removed? (M-D-Y H:M)	text (datetime_mdy)
111	ease_sponge_remove_2 Show the field ONLY if: [randomized_yn] = '1' and [xst at_attempted] = '1' and [surg_ proc_wound[2]] = '1' and [xsta t_used_wound_2] = '1'	Please describe the ease of sponge removal	radio 1 Failed to remove all sponges 2 Reasonably easy to remove all sponges 3 Sponges easily removed
112	time_sponge_removal_2 Show the field ONLY if: [randomized_yn] = '1' and [xst at_attempted] = '1' and [surg_ proc_wound[2]] = '1' and [xsta t_used_wound_2] = '1'	Please estimate the time required to remove the sponges	radio 1 31 minutes or longer 2 Between 5 and 30 minutes 3 Less than 5 minutes
113	imaging_sponge_removal_2 Show the field ONLY if: [randomized_yn] = '1' and [xst at_attempted] = '1' and [surg_ proc_wound(2]] = '1' and [xsta t_used_wound_2] = '1'	Please describe what intraoperative imaging was used to ensure removal of the sponges	radio 1 Imaging not used due to patient's condition 2 Imaging not used, as not available 3 Imaging not used, as deemed unnecessary 4 Imaging used
114	Imaging_outcome_2 Show the field ONLY if: [randomized_yn] = '1' and [sst at_attempted] = '1' and [srt proc_wound[2] = '1' and [ima ging_sponge_removal_2] = '4' and [ixstat_used_wound_2] = '1'	Describe the outcome	radio 1 Additional sponges were seen on imaging 2 No additional sponges were seen on imaging

115	xstat_satisfaction_2 Show the field ONLY if:	Please describe your overall satisfaction with the XSTAT device	radio 1 Dissatisfied
	[randomized_yn] = '1' and [xst at attempted] = '1' and fourg		2 Neither satisfied nor dissatisfied
	proc_wound(2)] = '1' and [xsta t_used_wound_2] = '1'		3 Satisfied
116	form_7_operative_treatment_	Section Header: Form Status	dropdown
	complete	Complete?	0 Incomplete
			1 Unverified
			2 Complete
Instr	rument: Form 8: Blood/Blo	od Product Transfusion Record (form_8_bloodblood_pro	duct_transfusion_record)
117	header_f8		descriptive
118	red_cell_units	Red cell concentrate (units)	text (integer) Field Annotation: @DEFAULT="0"

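### Section 5.2 requires a radiographic survey for retained sponges, but 8.4.2 and Form 7 accept imaging judged unnecessary as an ordinary answer, so asymptomatic retention could be under-counted

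*Protocol*

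**What the plan says.** Section 5.2 (Intervention to be evaluated) makes imaging a requirement: "a radiographic survey must be undertaken to identify any retained sponges". The reasons given are that some sponges may not be deployed and some may be dislodged when the patient is moved. The section names no exception, time or place. It supports the requirement with a case series that "identified retained sponges in two out of ten patients on initial post removal x-rays", and notes that "Each XSTAT[®] device consists of 38 sponges"; each trial pack holds two devices.

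Section 8.4.2 (Usability) gives four answers on imaging: not used because of the patient's condition, not used because unavailable, "Imaging deemed unnecessary", and used. Appendix 2, Form 7, repeats the list for each wound in fields 97 and 113, with the third answer worded "Imaging not used, as deemed unnecessary". The form's question is narrower than 8.4.2: "Please describe what intraoperative imaging was used to ensure removal of the sponges". Field 95 (field 111 for a second wound) also asks the surgeon about ease of removal, with "Failed to remove all sponges" as one answer.

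Retention beyond the first operation is a named safety outcome in 7.3(e) and 8.4.7(e). Section 10.3 reports the incidence of each prespecified adverse event and does not link retention to whether the survey was done.

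**The concern.** Section 5.2 asks for imaging because the surgeon may be unable to tell that every sponge is out. An answer that records imaging as unnecessary rests on exactly that judgement. A site reading 8.4.2 or completing Form 7 could reasonably conclude that the survey is at the surgeon's discretion.

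Two things are at stake. The first is patient safety: section 13.2 names sponges that go unseen as a route to retention, with infection and pain as possible results, and section 14.3.2 lists overlooked sponges as an anticipated device effect. The second is ascertainment. A patient who was never imaged and has no symptoms enters the 10.3 incidence as a patient without retention. That error makes the device look safer than it is, on an outcome that belongs to Objective 5.

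**Working it through.** The protocol states no rate or sample-size figure that depends on this point, so there is nothing of its own to reproduce. The check is mainly a comparison of texts.

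1. **Requirement.** Section 5.2 uses mandatory wording and states no exception. The only timing words nearby describe the cited series, not the trial.

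2. **Recording in 8.4.2.** Three of the four answers are reasons for not imaging. Patient condition and unavailability read naturally as recorded departures from a rule. A judgement that imaging was not needed is harder to read that way. Section 8.4.2 does not say that the item concerns intraoperative imaging only.

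3. **Recording in Form 7.** Fields 97 and 113 ask about intraoperative imaging. The imaging result (fields 98 and 114) appears only if imaging was used. As printed, the display conditions show all of these fields only where an operation on that wound is recorded. A patient treated with XSTAT who had no such operation would leave no imaging record there. Codebook fields 53 to 83 are not visible, so a field for a later film may exist.

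4. **Deviation handling.** Field 14 asks for the reason for a protocol violation when a patient randomized to XSTAT did not have the treatment attempted. No comparable prompt is visible for an omitted survey, and no section text calls the omission a deviation.

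5. **Other ways to find a sponge.** These are the surgeon's report in field 95 or 111, the safety data to 7 days or earlier discharge (8.4.7), and adverse-event reporting to discharge (14.2). They can find a sponge known to have been left, or one that causes trouble in that time. An overlooked sponge without symptoms can escape all three.

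6. **Why a count cannot replace the survey.** A full pack holds 2 × 38 = 76 sponges. Section 5.2 says that not all may be deployed and some may be dislodged, so the number removed cannot be set against a known number in the wound.

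7. **The only rate in the protocol.** The cited series gives 2/10 = 20%. The exact (Clopper-Pearson) 95% limits are:
   - lower: the 0.025 quantile of Beta(2, 9) = 0.0252
   - upper: the 0.975 quantile of Beta(3, 8) = 0.5561

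   The interval is 2.5% to 55.6%. This rate cannot be turned into an under-count for the trial. It is the rate of sponges on the first x-ray after removal, whereas 7.3(e) counts retention beyond the first operation. A sponge seen on intraoperative imaging and taken out at once never becomes a 7.3(e) event. The series was in-hospital use, and the protocol gives no expected number of patients without imaging.

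**The case against.** The strongest reply is that the texts do different jobs. Section 5.2 sets a procedure. Section 8.4.2 and Form 7 record what happened, and a form must be able to record that something was not done. Because Form 7 asks about intraoperative imaging, a surgeon could truthfully call that unnecessary and still meet 5.2 with a later film. This stands as far as it goes: a reader might infer that the protocol contradicts itself or formally waives the survey, and the documents do not support that. What remains is that neither 5.2 nor 8.4.2 says a later film is what is meant.

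A reader might also take 7.2.2(c) as making imaging optional, or take the lack of a survey row in Table 1 as proof that none is planned. Neither follows. Section 7.2.2(c) lists "The use of x-rays/image intensifiers to ensure complete removal of the sponges" as something to be measured, which agrees with 5.2. Table 1 schedules data, not procedures.

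It can further be said that study monitors look for violations (15.2), that training covers sponge removal (15.1.1), and that a procedures manual, not shown, defines the variables (15.1.2). These help, but monitors and trainers work from the same mixed message. Finally, how retention is tabulated could be left to a statistical analysis plan. That is fair for the layout of a table. Whether the survey is done and recorded is protocol content, and no analysis plan can recover a film that was not taken.

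**Conclusion.** The point holds as an ambiguity with a consequence for safety and ascertainment. A required survey is recorded in a way that lets sites treat it as discretionary, and the retention incidence does not show who was surveyed. Any resulting error in detection runs towards too few retained sponges.

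The size is not estimable from the documents. A reader might infer that about 20% of un-imaged patients would carry a missed sponge, or that the reported rate would fall in proportion to the share imaged. The first treats a different endpoint from an in-hospital series of ten as the trial's own. The second assumes that imaging is the only way to find a sponge, which 8.4.7, 14.2 and the surgeon's report contradict.

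The conclusion assumes that some sites would act on the discretionary answer and that the codebook fields not visible do not already settle the matter. Confidence is medium. The change should be made because it is cheap and concerns patient safety. The trial is a pilot of at most 50 patients, and section 10.3 attaches no decision rule to the retention rate.

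**What to change.** - **Sections 5.2 and 8.4.2:** state that every patient in whom XSTAT was used, whether or not a removal operation took place, has a radiographic survey before discharge, intraoperative or postoperative. State that the answer judging imaging unnecessary refers only to intraoperative imaging and does not waive the survey. State that an omitted survey is recorded as a deviation with its reason, for example death before it could be done.
- **Form 7:** keep the existing answers in fields 97 and 113. If no existing field records a postoperative film, add one that is also available for patients without an operation.
- **Section 10.3:** report retention over all XSTAT-treated patients, give the number surveyed beside it, and list unsurveyed patients separately.

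The cost is a few sentences across three sections and at most one form item. The downside is slightly more deviation logging and one extra reporting line. No imaging is added beyond what 5.2 already requires.
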